**Target population:** In general we will aim to increase generalisability by using the minimum number of entry criteria. The task of establishing an adolescent target population based on the status of being on the edge of care is a challenging one as, in most contexts, this term gestures towards a heterogeneous group. At the same time, we also recognise that the referral routes of Forensic, Social Services, CAMHS or Education often identify the same young people and families with very similar needs when they have reached a particular crisis point. The quality of the crisis may be associated with the specific service (e.g. forensic services are triggered by convictions, education services by repeated school exclusions) but the underlying causes in terms of family disorganisation combined with antisocial behaviour by the young person are similar and the outcomes in terms of risk of out of home care are shared.

Taking this into consideration we have defined four alternative inclusion criteria for eligibility for randomisation into MST or MAU depending on the source of the referral. We are confident based on our shared clinical experience that the families identified in these routes will be similar and that the target population will be a relatively homogenous one. They will share at least 3 of the following features indicative of 'risk status' that can be considered severe and which serve as generic inclusion criteria: (a) Excluded or at significant risk of school exclusion; (b) High levels of non attendance at school (c) An offending history or at significant risk of offending; (d) Previous episodes on the Child Protection Register; (e) Previous episodes of being looked after; (f) Previous referral to FGC to prevent young person from becoming looked after; (g) History of siblings being looked after. We will put in place demographic, clinical and family functioning measures to assess these attributes and test the assumption of relative homogeneity notwithstanding different referral paths. We hope that at most sites a multi-agency panel will consider referrals. Referrals considered suitable by the panel will be included in the trial if they meet the following general inclusion criteria: (1) Young person aged 11-17 years; (2) Sufficient

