family involvement for MST to be applied, excluding adolescents already in local authority care or foster accommodation unless this is a long term placement of over 3 years. For sufficient family involvement to be applied an adult primary caregiver needs to be clearly identified as having a long-term commitment to that YP in providing care. If that young person cannot reasonably be defined as having a long-term parenting figure, for example, being placed in the care of a family friend or individual with no prior caretaking experiencing with that young person, then it should be clear how the parent or prior parenting figures remain part of the intervention. We would ask that the following considerations are borne in mind for each case - a) is the young person being placed with an adult figure who will provide sufficient family involvement and all that entails b) If this person is outside of the immediate family constellation, how will a family or extended family member remain involved; c) is there a credible plan for parenting that will persist beyond the intervention.

We discourage families to be entered in to the trial where there is no stable parenting figure in place, however in certain circumstances, when there is a clear plan for the young person to be placed immediately back in the home prior to randomisation i.e. if a young person has a short term admission to care/accommodation in either a residential or foster placement an exception will be made for them to be included., (3) No existing agency involvement (e.g. the family is already engaged with a therapist) which would interfere with MST and (4) Meets ONE of the following set of criteria indicating suitability for MST: (a) Persistent (weekly) and enduring (6 months or longer) violent and aggressive interpersonal behaviour OR (b) A significant risk of harm to self or to others e.g. self harming, substance misuse, sexual exploitation, absconding, OR (c) at least one conviction and three warnings, reprimands or convictions in the last 18 months; OR (d) current diagnosis of externalising disorder and a record of unsuccessful outpatient treatment, OR (e) permanent school exclusion.

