MST. This is a potential source of bias and could, if criteria interact with suitability, generate builtin between site differences. We intend to use the expertise that we have built up both in London and in Cambridge to work with each multi-agency panel and create a homogenous recruitment protocol for the panels to work to which would also be consistent with the eligibility criteria for the trial. We are currently in discussion with the sites regarding this protocol. The key components of such a protocol would include a standard referral form including information pertaining to inclusion and exclusion criteria which will form the first screen to the trial focusing on establishing severity and chronicity. Following the acceptance of the referral by the Panel, a standard initial letter in the first language of the family from the multi-agency panel will be sent to parents and separately to the young person if s/he is 16, informing them about the trial, standard explanatory visit and a standard consenting procedure. Recruitment begins with this letter which would be sent to all those identified by a panel to be probably suitable for MST. The letter from the panel (or the MST referral team) would invite participation, and informs families and the young person that someone from the MST team (preferably the MST supervisor) will contact them unless they do not wish to participate in the trial. The letter would include material in age and culturally appropriate language in the form of a leaflet for both the parents and the young person explaining the trial and what involvement in the trial would mean at that particular site. Information sheets have been constructed and designed with input from young people and their parents/carers who have used MST in order to make them as useful and accessible as possible. Separate, specifically adapted sheets are included for different age ranges; one for children aged 11-15 and one for young people aged 16-17, containing the same information as the parent/carer sheet but in age-appropriate language. Information sheets have been constructed and designed with input from young people and their parents/carers who have used MST in order to make them as useful and accessible as possible. The MST supervisor and therapist will be on hand at consent meetings to explain anything in the information sheets and consent forms that is unclear. After a brief period of time (1-2 weeks) the family would be contacted by a member of the MST team to explain in person what participation might involve and to arrange an appointment. This is the second stage of the multiple gating procedure and the MST worker might identify exclusion criteria at this stage (e.g. risk of possible injury to worker, incompatible agency involvement, severe substance dependence). Consent forms would not be signed at this appointment because experience has shown that actual take-up of treatment increases dramatically and early dropouts are reduced if the family feels they have been given adequate time to consider their participation. Unless the family expresses a decision not to participate at the time of the visit, a phone contact would be made by the OA no less than 3 days after MST and the trial have been explained to families or within 7 days should the family wish for more time to think about the trial. This would be the time for reviewing the consent form and if signed. completing pre-randomisation questionnaires and measures. At this second visit, the final evaluation for eligibility is made (screen 3). When all the instruments have been completed and trial eligibility confirmed, the OA makes a call to the trial centre to obtain the allocation.

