
The ethical principles of which the MST Supervisor, MST Therapists and Outcomes Assessor must be aware when speaking to the young person and his or her carer about participation in the study are:

There is no negative consequence for those who decline to participate;

There is no negative consequence for those who do participate;

Potential participants are informed of all that is expected of them, including benefits and risks that may be associated with participation;

Consent to participate is freely and voluntarily given, with full appreciation of the above; Participants understand that they can withdraw their consent to continued participation at any point in the process;

All information gathered about them will remain confidential; and

Anonymity is assured in that individual participants will not be identified in any report or document produced.

Second, the MST Supervisor, MST Therapists and Outcomes Assessor understand that, for the MST clinical trial, the implications of these standards are that potential participants must understand:

What MST entails, including the amount of time spent in the home, the intensity and duration of intervention and what is expected of the participants;

That young people who decline to participate in the clinical trial will receive the same level of intervention they would normally expect from the YOS (i.e. they will not be penalised for declining consent);

That half those who sign the consent forms will receive whatever intervention would have been available to them if no MST study had been underway;

That the decision about who gets MST is made randomly so each person has an equal chance of being selected;

That the services offered to the control group are not a placebo or are not inferior but rather constitute the typical services available to young offenders as MAU;

That participation in the clinical trial entails filling out questionnaires to gather background information and after discharge from treatment or approximately five months if not allocated to MST;

That the young person's school will be approached for information;

That the parent or carer and the young person are free to drop out of the MST condition;

That all information participants provide will remain confidential except in three circumstances: 1) A person under 16 is at risk as defined in the Children Act 1989

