2) a person voices a fixed intention to harm a specific other person that must be communicated to the police; or 3)the information is demanded by the judge; and

That at six-month, one-year, two-year and three-year intervals the law-breaking behavior of the young person will be checked and that this information will not be revealed to anyone outside the research group.

The verbal explanation of the study given by the MST Supervisor, MST Therapists and Outcomes Assessor to the young person and her/his parent or carer is a crucial part of the process whereby they are able to give valid consent to take part in the study. In seeking consent, the MST Supervisor, MST Therapists and Outcomes Assessor ensure the decision is made on an informed basis. Due to the vulnerability of the young person and her/his parent or principal carer, there are a number of potential misunderstandings that could lead to their giving consent on an uninformed basis and to which the MST Supervisor, MST Therapists and Outcomes Assessor must be alert, namely:

1. The young person and her/his parent or carer may think they are obliged to take part because the study is part of the young person's sentence, i.e. they may not understand the voluntary nature of the study.

2. They may think that refusal to participate will have further negative consequences for the young person.

3. They may think that if they drop out of the study that this will have negative consequences for the young person, for instance that the young person will be breached and taken back to court.

4. They may think that agreement to participate means that they automatically get MST.

5. They may not understand that the MST intervention involves the participation of the parent or carer as well as the young person.

6. The young person and his/her parent or carer may not realise the young person's decision as to whether to participate carries the same weight as the parent or principal carer and that, if the young person refuses to give consent, participation cannot go ahead even if the parent or carer agree to give their consent.

7. The capacity of the young person to understand the nature of the study will vary accoriding to her/his age. For example, a young person aged 13 years is unlikely to understand or grasp the nature of the study in the same way as a young person aged 16 years.

To guard against these and other pitfalls MST Supervisor, MST Therapists and Outcomes Assessor considers the following action points:

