#### Participant Adherence:

Dropping out of treatment is common during interventions for antisocial problems (Kazdin & Wassell, 2000; Kazdin & Wasser, 2000) MST has a far superior record of maintaining cases in treatment when compared with MAU (86% vs 79%). Based on 6 studies the RR is highly significantly favouring MST (RR=.69, 95% CI: 0.49, .98). In the BCT following the careful recruitment procedure outlined above, well over 90% of those recruited for either arm of the trial have been retained for the purposes of data collection. We recognise that participation in the various treatment protocols will have lower adherence than data collection as data collection visits are incentivised for both families and young persons by modest compensation for time and travel. To ensure a comprehensive intent to treat analysis the primary outcomes consist of data recorded formally (e.g. out of home placements) which can be measured even if participants have dropped out of treatment and research appointments. In the current trial we have conservatively assumed a 5% dropout at each measurement point, totalling a 15% attrition overall that would effect analysis of secondary outcomes (see Figure 2).

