#### **Measures:**

Follow-up assessments will be at 6, 12, 18, 24, 36 and 48 months post randomisation, with primary outcomes collected until 5 years post randomisation.

(a) Principles of measurement: The measures will be made across multiple domains (specific to criminal behaviour, family function, user satisfaction, comorbid problems and economic costs), using multiple methods (interviews, questionnaires, records), and multiple sources (adolescent, parent, teachers) to maximise the clinical validity of the outcome assessments and minimise bias arising from any single source of information. Where possible, measures will be made by individuals blind to treatment allocation. Many of the measures have been selected because they are part of an ambitious project under-way in the Parenting Academy (Scott, Dabbs et al.) with a range of samples, including with a large sample of looked after children, which will provide UK norms against which the current sample may be compared.

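### The confidentiality exception for a young person at risk ends at 16, although the trial enrols to 17 and follows younger entrants past 16

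*Protocol*

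**What the plan says.** All of the wording at issue is in the Protocol, under Methods of recruitment and consent. The ethical principles there begin from a default with no exception: "All information gathered about them will remain confidential". The list of what potential participants must understand then qualifies it: "all information participants provide will remain confidential except in three circumstances: 1) A person under 16 is at risk", with risk defined by reference to the Children Act 1989. The second exception applies where "a person voices a fixed intention to harm a specific other person that must be communicated to the police". The third is a demand by a judge. No fourth is given.

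The age range is wider than the first exception. Under Target population the general inclusion criteria begin "1) Young person aged 11-17 years". The information sheets recognise the older group separately: "one for children aged 11-15 and one for young people aged 16-17, containing the same information as the parent/carer sheet". One of the alternative suitability criteria is "A significant risk of harm to self or to others e.g. self harming, substance misuse, sexual exploitation, absconding". Under Measures, "Follow-up assessments will be at 6, 12, 18, 24, 36 and 48 months post randomisation".

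**The concern.** Participants are told a closed list of three exceptions. The list decides both what they believe when they consent and what assurance staff have given when a disclosure comes. If its only at-risk exception stops below the upper age of enrolment, the oldest entrants fall outside it from baseline, and younger entrants leave it as they age.

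Two things are at stake. The first is safety: faced with a 16- or 17-year-old who discloses serious self-risk or exploitation and refuses to have it passed on, staff find no ground in the list for acting. The second is consent: if staff act anyway, they break an assurance the Protocol required them to give, and the participant was never warned that they might.

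The assessments can bring out risk that no referring agency knows about. Depression is monitored by questionnaire (Measures), and psychiatric interviews are used both before and after 18 (Annual follow up from 2-5 years).

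**Working it through.** There is no stated figure to reproduce. The check has a textual part and an age calculation.

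**Exceptions against the case in question** (age 16-17, serious risk to self or exploitation, sharing refused)

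| Exception | Applies? | Reason |
|---|---|---|
| Person under 16 at risk | No | Age limit |
| Fixed intention to harm a specific other person | No | The risk is to the participant |
| Judge's demand | Only if a judge asks | Staff cannot start it |

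The rest of the Protocol gives no other disclosure route. The risks section covers accidental breach of confidentiality through data handling. The paragraph on expected serious adverse events covers serious injury, committee review of a death and contact with families. Research Governance mentions operating procedures for participant safety only in general terms.

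**How many assessments fall at 16-17**

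Inputs: baseline plus follow-up at 6, 12, 18, 24, 36 and 48 months, so t = 0, 0.5, 1, 1.5, 2, 3, 4 years (Measures); entry ages 11-17 (Target population); 700 participants (Procedure and Sample size). An assessment counts if 16 ≤ age at entry + t < 18.

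*Without any assumption on the entry-age distribution.* An entrant aged 11 is still under 16 at 48 months, so none count. An entrant aged 12 or over is at least 16 by 48 months. The largest gap between assessments is 1 year and the window is 2 years wide, so at least one assessment falls inside it.

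*Mean number at 16-17, with age uniform within each year of entry:*

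| Age at entry | Contributing assessments (years) | Mean |
|---|---|---|
| 11 | none | 0 |
| 12 | 4 | 1 |
| 13 | 3, 4 | 2 |
| 14 | half of those at 1.5; 2, 3 | 2.5 |
| 15 | half of those at 0.5; 1, 1.5, 2 | 3.5 |
| 16 | 0, 0.5, 1; half of those at 1.5 | 3.5 |
| 17 | 0; half of those at 0.5 | 1.5 |

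The sum is 14. With seven entry years and seven assessments each, the share is 14/49 = 0.286. For 700 participants: 700 × 7 = 4,900 assessments, of which 4,900 × 14/49 = 1,400 fall at 16-17.

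*With dropout.* Participant Adherence states that "we have conservatively assumed a 5% dropout at each measurement point", totalling 15% over three points. Extending that loss of 5 percentage points to all six follow-ups is my assumption. Retention is then 1, 0.95, 0.90, 0.85, 0.80, 0.75, 0.70, which sums to 5.95. Total: 700 × 5.95 = 4,165. Under uniform entry each time point has 2/7 of participants at 16-17, so 4,165 × 2/7 = 1,190, again 29%.

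*Other assumed entry-age ranges, each uniform:*

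| Entry ages | Complete follow-up | With dropout |
|---|---|---|
| 11-14 | 5.5/28 = 20% | 4.125/23.8 = 17% |
| 13-16 | 11.5/28 = 41% | 9.725/23.8 = 41% |
| 15-17 | 8.5/21 = 40% | 7.775/17.85 = 44% |

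**The case against.** The strongest reply is that the list is content for the consent discussion, not a safeguarding procedure. What staff do about a disclosure may be set out in operating procedures that are not shown. The 16-17 sheet, also not shown, may state the limits of confidentiality correctly. This stands as a limit: the defect shown is in the Protocol's own list, and the consent harm depends on what participants were actually told. It does not remove the point. The Protocol fixes what participants must understand, so if the sheets or procedures go further, the Protocol contradicts them and still needs correcting.

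Age 16 may also be a deliberate threshold, since the panel's letter is sent separately to the young person at 16 and the sheets divide there. The Protocol gives no such reason for the confidentiality limit, and it requires consent from a parent or carer with legal responsibility as well as from the young person.

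Some of the risk will already be known to agencies when it is the ground for referral. That is true, and it narrows the gap to new serious risk that the participant refuses to have shared.

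The visit counts do not measure harm, which is accepted. They also rely on the 48-month schedule. The objectives in the Trial Summary list assessments only to 36 months, and on that schedule an entrant aged 12 would have none at 16-17. The Overview, Measures and the section on annual follow-up all run to 48 months, so I have used that.

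Finally, the point changes no statistical result. That is correct and is not claimed.

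**Conclusion.** The concern holds. The Protocol's list leaves serious self-risk or exploitation at age 16-17, where sharing is refused, under no stated exception except a judge's demand. This is a rule set at the wrong age for the enrolled population, and it should be fixed for participant safety and valid consent.

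The exposure is not marginal. On the 48-month schedule it reaches every retained entrant aged 12 or over. The 29% figure is an illustration that rests on uniform entry ages; the 17% to 44% range shows how it moves with other entry ages and with dropout.

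The claim is limited. Staff can still act with the participant's agreement, no gap is claimed under 16, and the threshold for those aged 18 or over is a separate policy choice that is not part of this finding.

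**What to change.** In the list of what participants must understand, extend the at-risk exception from under 16 to every enrolled young person up to age 17, and name serious risk of harm to self and exploitation. Qualify the unconditional confidentiality statement in the ethical principles so that it refers to the list. Check the 11-15, 16-17 and parent/carer sheets and the outcome assessors' instructions against the new wording, and correct them only where they differ. Tell participants already enrolled at their next scheduled visit.

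The cost is a wording amendment, a document check and a short explanation at a visit already planned. Because the amendment changes a term participants accepted, the ethics committee should confirm that telling them at a visit is enough. The downside is small: a less absolute promise may slightly reduce disclosure or consent among older participants.
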